12 SAFETY REPORTING

12.1 Definitions

The Investigator is responsible for reporting all AEs that are observed or reported during the study, regardless of their relationship to study drug or their clinical significance.

An **AE** is defined as any untoward medical occurrence in a patient enrolled into this study regardless of its causal relationship to study drug. Patients or their legally authorized representatives will be instructed to contact the Investigator or Sub-Investigator at any time after signing the ICF if any symptoms develop.

A Treatment Emergent AE (**TEAE**) is defined as any event not present before exposure to study drug or any event already present that worsens in either intensity or frequency after exposure to study drug.

A Serious AE (**SAE**) is defined as any event that:

- Results in death,
- Is immediately life-threatening,
- Requires inpatient hospitalization or prolongation of existing hospitalization,
- Results in persistent or significant disability/incapacity,
- Is a congenital anomaly/birth defect,
- Significant medical event in the investigator's judgment (*e.g.*, may jeopardize the patient or may require medical/surgical intervention to prevent one of the outcomes listed above)

PD and disease-related death will not be considered an AE or SAE.

An **Adverse Drug Reaction (ADR)** is an AE, which is considered to be causally related to any dose of NUC-1031. This means that a causal relationship between NUC-1031 and the AE is at least a reasonable possibility, *i.e.* the relationship cannot be ruled out.

An **Unexpected Drug Reaction** is an adverse drug reaction, the nature or severity of which, is not consistent with applicable product information (referring to information in IB, see RSI).

A **Suspected Unexpected Serious Adverse Reaction (SUSAR)** is a serious adverse drug reaction, the nature or severity of which is not consistent with the applicable product information (*e.g.* Investigator's Brochure for an unapproved IMP).

Important medical events that may not result in death, be life threatening, or require hospitalization may be considered an SAE when, based upon appropriate medical judgment, they may jeopardize the patient and may require medical or surgical intervention to prevent one of the outcomes listed in this definition. Examples of such medical events include allergic bronchospasm requiring intensive treatment in an emergency room or at home, blood

dyscrasias, convulsions that do not result in inpatient hospitalization, or the development of drug dependency or drug abuse. Please consult [Section 12.5](#) for the specific mechanism by which SAEs are to be reported.

12.2 Adverse Event Reporting

At every study visit, patients will be asked nondirective questions to elicit any medically related changes in their well-being. They will also be asked if they have been hospitalized, had any accidents, used any new medications, or changed concomitant medication regimens (both prescription and over-the-counter medications). In addition to patient observations, AEs will be documented from any data collected on the CRF or other documents that are relevant to patient safety. Any allergic reaction to the agents administered as study drug treatment must be reported as an AE.

All AEs that occur from date of consent through 30 days after the last dose of study drug must be reported in detail on the AE CRF. Disease progression in the medical opinion of the physician and/or disease-related morbidity and mortality as a study endpoint will not be considered an AE or SAE but should be captured on the Death CRF. Information to be collected for each AE includes onset date, type of event, etiology, Investigator-specified assessment of severity and relationship to study drug, seriousness, any required treatment or evaluations, outcome and date of resolution. AEs resulting from concurrent illnesses, reactions to concurrent illnesses, reactions to concurrent medications, or progression of disease states must also be reported. All AEs will be followed for 30 days after the patient's last dose, or until resolution, whichever comes first.

Pre-existing conditions (present before the start of the AE collection period) are considered concurrent medical conditions and should not be recorded as AEs. However, if the patient experiences a worsening or complication of such a concurrent condition, the worsening or complication should be recorded as an AE. Pre-existing AEs that worsen should be followed until 30 days after the patient's last dose or resolution to the AE level present at study entry. Investigators should ensure that the AE term recorded captures the change in the condition (*e.g.* "worsening of [condition]").

Insufficient clinical response, efficacy, or pharmacological action should NOT be recorded as an AE. The Investigator must make the distinction between exacerbation of pre-existing illness and lack of therapeutic efficacy. PD is NOT an AE; however, some sequelae of PD (*i.e.* pain, neurologic impairment) may be reported as AEs (generally not related to NUC-1031).

Abnormal laboratory values or test results constitute AEs only if they induce clinical signs or symptoms, are considered clinically significant, require therapy or further diagnosis beyond repeat testing for confirmation, or (if not associated with clinical signs or symptoms) they remain at levels consistent with severe abnormalities despite appropriate medical intervention. It is requested that when reporting AEs for which potentially redundant NCI CTCAE terms exist, the Investigator utilizes the more clinically-oriented terminology (for example, 'anemia' is preferable to 'hemoglobin decreased').

It is also requested that in the setting of an allergic reaction or suspected allergic reaction considered by the Investigator to be related to NUC-1031, that the Investigator reports both the specific symptoms associated with the reaction (*i.e.* 'urticaria', 'dyspnea') and also report the appropriate term indicating the allergic reaction ('allergic reaction' or 'anaphylaxis' if appropriate [Immune System Disorders; CTCAE v4.03]).

12.3 Assessment of Causality

The Investigator's assessment of an AE's relationship to study drug is part of the documentation process, but it is not a factor in determining what is or is not reported in the study. If there is any doubt as to whether a clinical observation is an AE, the event should be reported.

The relationship of an AE to NUC-1031 should be classified using the following guidelines:

Related: A temporal relationship exists between the event onset and administration of NUC-1031. It cannot be readily explained by the patient's clinical state, intercurrent illness, or concomitant therapies. In case of cessation or reduction of the dose, the event abates or resolves and reappears upon rechallenge. This includes events that are considered possibly, probably, or definitely related to NUC-1031.

Not Related: Evidence exists that the AE has an etiology other than the study drug (e.g. pre-existing condition, underlying disease, intercurrent illness, or concomitant medication). This includes events that are considered probably not or not related to NUC-1031. It should be emphasized that ineffective study drug treatment should not be considered as causally related in the context of AE reporting (in other words, PD is not considered an AE; however some sequelae of PD may be reported as AEs and should generally be reported as AEs not related to NUC-1031).

12.4 Assessment of Severity

The severity of each AE is to be assessed by the Investigator according to NCI CTCAE, v4.03. If the AE is not included in the NCI CTCAE, then the Investigator is to determine the intensity of the AE according to the following criteria:

Mild (Grade 1):	AE that disappears or is easily tolerated on continuation of study drug.
Moderate (Grade 2):	AE sufficiently discomforting to cause interference with usual work activities.
Severe (Grade 3):	AE that is incapacitating, with inability to work or perform daily activities.
Life-Threatening (Grade 4):	AE that is potentially life-threatening*
Death (Grade 5):	Death related to AE.

*If a life-threatening (Grade 4) AE is *immediately* life-threatening, the event is, by definition, serious and is to be reported as described in [Sections 12.6](#) and [12.7](#).

12.5 SAE Reporting

Any AE considered serious by the Investigator or sub investigator or that meets the seriousness criteria that occurs from first administration of study drug through 30 days after last study drug dose must be reported to Chiltern Pharmacovigilance (PV) within 24 hours from the time study site personnel first learn about the event. The SAE report will be completed and emailed or faxed to Chiltern PV using the contact details in [Table 6](#).

Table 6 Chiltern pharmacovigilance contact details

Email	[contact]
UK fax number	([contact]
US fax number	(+1) [contact] or (+1) [contact]

If the patient is hospitalized because of or during the course of an SAE, then a copy of the hospital discharge summary (if available) should be faxed to Chiltern PV, using the fax numbers listed above, as soon as it becomes available. Withdrawal from the study and all therapeutic measures will be performed at the discretion of the Investigator or sub investigator.

NuCana, or Chiltern PV, will notify appropriate regulatory authorities of any unexpected, fatal, or life-threatening experience that is determined to be related to the use of the study drug. Refer to [Section 12.7](#) for more details.

The Investigator or sub investigator is responsible for informing the IRB/EC. Copies of SAE correspondence with all Investigators or sub-investigators, governing authorities, ethics committees, and NuCana must be submitted to Chiltern PV for filing.

A patient experiencing one or more SAE will receive treatment and follow-up evaluations by the Investigator or sub-investigator or will be referred to another appropriate physician for treatment and follow-up. All SAEs must be followed to resolution or, if resolution is unlikely, to stabilization.

Study endpoints in ovarian cancer patients include disease-related mortality and morbidity, which will not be reported as expedited IND safety reports, unless there is a serious and unexpected event with evidence of a causal relationship between study drug and the event. As appropriate and based on the frequency of occurrence, SAEs in the study will be reported to the FDA at an appropriate interval, such as inclusion in the periodic update IND annual report.

The following SAEs will not be reported individually in an expedited manner because they are anticipated to occur in the ovarian cancer study population receiving standard of care treatment at some frequency independent of study drug exposure:

- Progression of disease.
- Death as a consequence of the underlying malignancy.

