- 17.** For women of child-bearing potential, serum pregnancy testing must be performed within 72 hours prior to C1D1 and at End of Treatment visit. In addition, urine pregnancy tests will be performed pre-dose on Day 1 of each cycle. If any urine test result is positive, patient dosing will be postponed until the result is confirmed by a serum pregnancy test. Patients with a positive serum test will be discontinued from the study.
- 18.** Includes insertion of central venous access device, if not already present (if NUC-1031 is centrally administered).
- 19.** Optional fresh biopsy tissue sample collection within 24 hours post administration of C1D1 dose for patients who consent.
- 20.** Includes treatment discontinuation due to disease progression or early treatment discontinuation for other reasons (*e.g.* withdrawal of consent). Progressive disease should be confirmed prior to stopping treatment. Visit to occur within 30 (± 7) days of the last dose of NUC-1031.
- 21.** Patients withdrawing from the study with no radiological evidence of disease progression will receive scans every 8 weeks (± 7 days) from C1D1 until disease progression, initiation of a new treatment or death in order to determine duration of overall response and PFS.
- 22.** Adverse events should be captured from the time of consent up to 30 days after the last dose of NUC-1031. SAEs deemed definitely, probably or possibly related to NUC-1031 but outside of this window (>30 days from last dose of NUC-1031) should also be captured in the eCRF.
- 23.** Patients with evidence of disease progression as defined by RECIST criteria will receive a phone call at regular intervals (every 12 weeks ± 7 days) until death, loss to follow-up, or study discontinuation in order to determine duration of Overall Survival.

ABBREVIATIONS

°C	Degrees Centigrade
AE	Adverse event
ALT	Alanine aminotransferase
ANC	Absolute neutrophil count
AST	Aspartate aminotransferase
AUC	Area under the curve
AUC _{0-t}	Area under the plasma concentration-time curve from time zero to the last measurable concentration
BICR	Blinded Independent Central Reviewer
BRCA 1/2	Breast cancer (gene) 1/2
BUN	Blood urea nitrogen
CA125	Cancer Antigen 125
CDA	Cytidine deaminase
CL	Apparent clearance
C _{max}	Maximum plasma concentration; peak plasma concentration
CNS	Central Nervous System
CR	Complete Response
CRF	Case report form
CRO	Clinical Research Organization
CSR	Clinical study report
CT	Computed tomography

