5.1.1 Informed Consent for Tumor Tissue Collection

A fresh tumor biopsy and archival tumor tissue, if available are required assessments for this study. Patients who do not have easily accessible tumor for biopsy should not be put at undue risk for sample collection and these patients remain eligible for the study. Biopsied lesions should not be designated as target lesions for the purposes of RECIST.

An optional tumor sample may also be collected within 24 hours of NUC-1031 administration on C1D1. Participation in this element of the research requires patients to sign an addendum to the ICF. For sampling procedures, storage conditions, and shipment instructions, please refer to the accompanying Tumor Tissue Laboratory Manual.

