- Tumor imaging (CT, MRI and/or PET-CT [US only] of thorax, abdomen and pelvis) – performed within 28 days of randomization. Biopsied lesions should not be designated as target lesions for the purposes of RECIST.
- Obtain fresh and archival tumor tissue. For sampling procedures, storage conditions, and shipment instructions, see the Tumor Tissue Laboratory Manual. Patients who do not have easily accessible tumor for biopsy should not be put at undue risk for sample collection and these patients remain eligible for the study. Biopsied lesions should not be designated as target lesions for the purposes of RECIST.
- Recording of concomitant medication.

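### The 24-hour SAE duty in protocol section 12.5 stops 30 days after the last dose, while section 12.7 obliges the sponsor to report every SUSAR without time limit; serious pre-dose biopsy complications also fall outside it

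*Protocol*

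**What the plan says.** Section 12.5 sets the site's duty to notify pharmacovigilance. It covers a serious event "that occurs from first administration of study drug through 30 days after last study drug dose must be reported", within 24 hours of site staff learning of it.

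Recording is wider than notification. Section 12.2 states: "All AEs that occur from date of consent through 30 days after the last dose of study drug must be reported in detail", meaning on the AE CRF. Note 22 to the Summary Schedule of Events gives the same start and end, and then adds SAEs judged definitely, probably or possibly related to the drug that fall "outside of this window (>30 days from last dose of NUC-1031) should also be captured in the eCRF". It mentions no report to pharmacovigilance.

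Section 12.7 obliges the sponsor or its pharmacovigilance provider to report all SUSARs to authorities and ethics committees. Fatal or life-threatening ones are due within 7 days of receipt and the others within 15. It states no limit on when the event may have occurred.

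On the biopsy, section 5.1.1 says: "A fresh tumor biopsy and archival tumor tissue, if available are required assessments for this study". The exception follows at once: "Patients who do not have easily accessible tumor for biopsy should not be put at undue risk for sample collection". Section 5.3 places the procedure at screening: "Obtain fresh and archival tumor tissue".

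**The concern.** A SUSAR system works only if the site's duty to send is at least as wide as the sponsor's duty to assess and report. Here it is narrower. A cytotoxic drug can cause serious harm that shows itself after day 30, and note 22 accepts this by asking for such events. If they travel only through the eCRF, the expedited-reporting clock may start late, because it runs from receipt and nothing fixes when receipt happens.

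The pre-dose period raises a lesser form of the same question. The protocol requires an invasive procedure of some patients before they receive any drug, records what follows as AEs, and yet does not ask sites to notify a serious complication promptly. At stake in both cases is the speed of safety review. The primary analysis of response is not affected.

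**Working it through.** No figure in the plan needs reproducing. The check compares the windows.

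| Provision | Who acts | Start | End | Deadline |
|---|---|---|---|---|
| 12.2 and note 22, AEs | site, CRF | consent | 30 days after last dose | none stated |
| Note 22, late related SAEs | site, eCRF | after day 30 | none | none stated |
| 12.5, SAEs | site to pharmacovigilance | first dose | 30 days after last dose | 24 hours |
| 12.6, expedited reporting | site to pharmacovigilance | none of its own | none of its own | 24 hours |
| 12.7, SUSARs | sponsor to authorities | no window | no window | 7 or 15 days from receipt |
| 14.2, monitoring | monitor confirms SAEs were forwarded | no window | no window | none stated |

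**Late related SAEs.** Take an unexpected, drug-related SAE that is neither fatal nor life-threatening.
- Onset inside the 12.5 window: from site awareness to the authority takes at most 24 hours + 15 days = 16 days.
- Onset after day 30: the same path takes x + 15 days, where x is the time until pharmacovigilance receives the event. No provision bounds x.

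Sites can be expected to meet such events. The End of Treatment visit is allowed at 30 ± 7 days after the last dose, so up to day 30 + 7 = 37, and it includes AE recording (section 5.5.7). An SAE with onset on days 31 to 37 can thus be found at a scheduled visit and still lie outside section 12.5. After that, patients without progression return every 8 weeks, and the schedule's AE row carries note 22 at those visits.

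**Pre-dose SAEs.** Section 5.2 allows screening within 28 days of randomization and treatment up to 10 days after registration. The stretch from consent to first dose is then about 28 days. It reaches 28 + 10 = 38 days only if registration falls on the day of randomization, which the protocol does not state, and dosing starts on the last allowed day. A serious biopsy complication in that time is an AE under section 12.1, which disregards causality, and is recorded under section 12.2. It precedes the first dose and so lies outside section 12.5.

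**Does another provision close the gap?**
- Section 12.6 is framed for SAEs that need reporting, which leads back to section 12.5.
- The footnote in section 12.4 sends immediately life-threatening events to sections 12.6 and 12.7 with no window, but covers only that subset.
- Section 6.3 concerns following SAEs to resolution after consent withdrawal, not first notification.
- Section 12.10.3 exempts planned admissions, not complications arising from them.

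None gives sites a general duty outside the 12.5 window.

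**The case against.** The best defence is that the protocol openly separates CRF recording from the 24-hour channel, and that starting the channel at first dose is a legitimate choice. Section 12.7 already binds the sponsor for late SUSARs, and also expedites other safety issues that could change the conduct of the study, which might include a biopsy signal. Section 12.6 wants fatal or life-threatening SAEs notified immediately, and section 14.2 has monitors check that SAEs were forwarded. Nothing in section 12.5 forbids sending an event from outside its window.

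Much of this stands. Read generously, sections 12.4 and 12.6 cover life-threatening events at any time. That leaves SAEs that are serious for other reasons, such as hospitalization or disability. The duties in sections 12.7 and 14.2 fall on the sponsor and the monitor, so they expose the mismatch without curing it. For the pre-dose part taken alone, the first-dose start is closer to a design choice than to an error.

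Three stronger readings are tempting, and the protocol does not support them:
- *That biopsy complications escape SUSAR assessment.* Section 12.1 defines a SUSAR as a reaction to NUC-1031, so an event before any dose cannot be one.
- *That the harm is hidden.* Section 13.5.6.1 lists all SAEs with pre-treatment, ongoing or post-treatment status at onset. Only the summary tables leave out events outside the treatment-emergent period.
- *That these events are not sent.* The protocol sets no duty or deadline to send them; sites may still do so.

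**Conclusion.** The point holds as a mismatch between provisions. Its main part is the late related SAE: section 12.7 makes the sponsor answerable for SUSARs at any time, while section 12.5 and note 22 together give sites no duty or deadline to send those arising after day 30. That gap is open-ended.

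The secondary part is the pre-dose biopsy complication, in a window of about 28 days, or at most about 38 under the assumption given above. It concerns only patients with easily accessible tumor, and what is lost is prompt pharmacovigilance review, not regulatory reporting or visibility in the results. The optional biopsy after the first infusion is already inside the 12.5 window.

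The protocol gives no rate for either kind of event, so no expected number can be stated. In a study of up to 64 patients it is likely to be small. The conclusion rests on the written duties alone; separate safety-management instructions, if they exist, are not part of this document. It should be corrected because it concerns patient safety and the correction is cheap.

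**What to change.** Reconcile sections 12.5, 12.6, 12.7 and 14.2 and note 22 to one SAE reporting window. The 24-hour site duty should cover:
- SAEs between consent and first dose that are related to protocol-required procedures;
- all SAEs from first dose to 30 days after the last dose, as now;
- SAEs considered related to NUC-1031 at any time after day 30.

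Note 22 should say that late related SAEs go to pharmacovigilance as well as into the eCRF. Section 12.6 should refer to the single window, and the monitoring check in section 14.2 should use it too.

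The cost is amendment wording and a few additional SAE reports. No dose, endpoint, sample size or analysis changes.

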12.6 Expedited Reporting of SAEs

The following SAE reporting requirements apply regardless of the Investigator's assessment of the causality or expectedness of the SAE. If an SAE occurs that requires reporting, a SAE

Report Form should be completed and faxed within 24 hours of Investigator awareness to the Chiltern PV contact details provided above.

If the SAE has not been reported within the specified timeframe, a reason for the delay must be provided when sending the SAE Report Form. SAEs that are fatal or life-threatening must be notified immediately. For all SAEs, the Investigator is obliged to pursue and provide all required information in accordance with the timelines provided above.

